6.2 Admission (Visit 00B) (Day -1)

Subjects will be admitted to the confinement/hospital unit on Day -1 (Visit 00B). The following procedures are to occur on the Admission Day:

- Review inclusion and exclusion criteria.
- Obtain interim medical/surgical history, including an assessment for new medical conditions and symptoms by interview of subjects and note any changes since the previous clinic visit.
- Complete physical examination.
- Record concomitant medications including name and total daily dose of all prescription drugs, herbal products, vitamins, minerals, and over-the-counter medications. Per exclusion criteria, determine if concomitant medications could exclude subject from study.
- Record a resting (5-minute rest period) 12-lead ECG. May be performed within 72 hours of admission to the confinement unit.
- Record vital sign measurements (sitting blood pressure, sitting heart rate, weight, and oral body temperature).
- Urine pregnancy test for females of childbearing potential.

- Draw a fasting (2 hour) blood sample for clinical chemistry tests. May be performed within 72 hours of admission to the confinement unit.
- Draw blood samples for the following (these can be drawn with fasting draw for chemistry tests) May be performed within 72 hours of admission to the confinement unit.
 - Hematology tests.
 - Coagulation parameter: INR.
- Alcohol breath test or other suitable test for alcohol (e.g., blood alcohol test).
- Collect urine sample for urinalysis and drugs of abuse (amphetamines, barbiturates, benzodiazepines, cocaine metabolites, opiates, cannabinoids, and phencyclidine (PCP)).

If screening laboratory tests are performed within 72 hours of admission to the confinement/hospital unit, the tests do not have to be repeated with the exception of the urine pregnancy test for females of childbearing potential and the urine drug screen for all subjects, which will be repeated. If a subject meets eligibility criteria and is admitted, but is not dosed, the subject could be re-evaluated for participation in the study. If subject is re-evaluated within 3 months of serologic testing, serology testing (HIV, HCV, HBsAg) will not be repeated. The subject's history will be reviewed to ensure they do not have any new risk factors since the last serological testing that would predispose them to hepatitis or HIV.

6.3 Planned Study Visits

6.3.1 Dosing (Visit 01) (Day 1) and Confinement/Hospitalization (Visit 01A to Visit 01J) (Day 1 and Day 2)

Prior to dosing on Day 1, subjects will have pharmacokinetic samples collected (10 minutes pre-dose) and vital signs (sitting blood pressure, sitting heart rate, weight, and oral body temperature) obtained (30 minutes pre-dose). Subjects will then be administered a single oral 200 mg tablet of Pretomanid the morning of Visit Day 1 with 240 mL of water following an overnight fast, and the AE and SAE assessment period will begin. Vital signs (sitting blood pressure, sitting heart rate, and oral body temperature) will also be obtained 30 minutes after dose administration. Events that occur between the time of consent and administration of study drug will be recorded in the medical history. Subjects will be confined in the confinement/hospital unit overnight. Subjects will be discharged after assessments on Day 2 are completed (the 36-hour PK sampling time point).

After dosing, subjects will be assessed at 1, 2, 4, 5, 6, 8, 12-, 16-, 24- and 36-hours post-dose. For each assessment, the PK sample will be collected, AEs and SAEs will be assessed, and vital

signs (sitting blood pressure, sitting heart rate, and oral body temperature) will be recorded. A supine blood pressure will be obtained if the sitting blood pressure is abnormal. Weight will be collected at the 36-hour sampling time point. Instruct the subjects to volunteer any information regarding AEs/SAEs at any time during the study or query the subjects with an open question regarding any AEs/SAEs they may be experiencing (for example, “How do you feel?”), and document the findings.

Approximately 36 to 48 hours after the dose, depending on site preference, subjects will be discharged.

At 36 hours:

- Draw a fasting (2 hours) blood sample for clinical chemistry tests. This laboratory can be performed prior to the 36-hour post-dose draw to ensure fasting.
- Draw blood samples for the following (these can be drawn with fasting draw for chemistry tests):
 - Hematology tests
 - Coagulation parameter: INR
 - Collect urine samples for urinalysis.

Depending on site preference, participants may be discharged from the confinement/hospital unit.

6.3.2 Follow-up (Visits 02, 03, and 04) (Day 3, Day 4, and Day 5)

Subjects discharged at Day 2 will return for a follow-up visit on Day 3 (Visit 02). Subjects remaining in the confinement/hospital unit at Day 2 will complete all Day 3 (Visit 02) procedures as outlined for all subjects. After completion of Day 3 procedures those participants may be discharged from the hospital/confinement unit.

All subjects will return for follow-up visits on Days 4 (Visit 03) and 5 (Visit 04).

The following procedures are to occur on Days 3 (Visit 02), 4 (Visit 03) and 5 (Visit 04):

- Obtain interim medical/surgical history, including an assessment for new medical conditions and symptoms by interview of subjects and note any changes since the previous clinic visit.
- A targeted review of body systems will be obtained at these visits focused on liver disease and will include questions pertaining to development of ascites, jaundice, pruritis,

gastrointestinal bleeding, and encephalopathy. If the subject answers yes to any of these questions, a targeted physical exam will be performed.

- Record concomitant medications including name and total daily dose of all prescription drugs, herbal products, vitamins, minerals, and over-the-counter medications. Per exclusion criteria, determine if concomitant medications could exclude subject from study.
- Record vital sign measurements (sitting blood pressure, sitting heart rate, weight, and oral body temperature).
- Obtain blood sample for PK analysis.
- Information regarding AEs/SAEs will be assessed and recorded on the appropriate data collection form.
- Day 5 (in addition to the assessments listed above):
 - Draw a fasting (2 hours) blood sample for clinical chemistry tests
 - Draw blood samples for the following (these can be drawn with fasting draw for chemistry tests):
 - Hematology tests.
 - Coagulation parameter: INR.
 - Collect urine samples for urinalysis.

6.3.3 Final Study Visit (Visit 05) (Day 12)

The final study visit will occur 11 days after Pretomanid administration. The following procedures are to occur on Day 12:

- Complete physical examination.
- Obtain interim medical/surgical history, including an assessment for new medical conditions and symptoms by interview of subjects and note any changes since the previous clinic visit.
- A targeted review of systems will be obtained at these visits focused on liver disease and will include questions pertaining to development of ascites, jaundice, pruritus, gastrointestinal bleeding, and encephalopathy.
- Record concomitant medications including name and total daily dose of all prescription drugs, herbal products, vitamins, minerals, and over-the-counter medications. Per exclusion criteria, determine if concomitant medications could exclude subject from study
- Record a resting (5-minute rest period) 12-lead ECG.

- Record vital sign measurements (sitting blood pressure, sitting heart rate, weight and oral body temperature).
- Draw a fasting (2 hours) blood sample for clinical chemistry tests.
- Draw blood samples for the following:
 - Serum pregnancy test for females of childbearing potential.
 - Hematology tests.
 - Coagulation Parameter: INR.
- Collect urine samples for urinalysis.
- Information regarding AEs/SAEs will be assessed and recorded on the appropriate data collection form.

6.3.4 Early Termination Visit

The following assessments will be performed at the early termination visit for subjects who withdraw, or are withdrawn or terminated from this study:

- Obtain interim medical/surgical history, including an assessment for new medical conditions and symptoms by interview of subjects and note any changes since the previous clinic visit.
- Complete physical examination
- A targeted review of systems will be obtained at these visits focused on liver disease and will include questions pertaining to development of ascites, jaundice, pruritis, gastrointestinal bleeding, and encephalopathy.
- All concomitant medications will be recorded on the appropriate data collection form.
- Information regarding AEs/SAEs will be assessed and recorded on the appropriate data collection form.
- Urine or serum pregnancy test.

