Adverse events leading to discontinuation of treatment included elevation of ALT and electrocardiogram (ECG) changes. For three subjects, all from the same study, the TEAE leading to discontinuation was increased ALT. The elevated transaminases were detected at a scheduled laboratory evaluation and in all three subjects the increased ALT was asymptomatic and ALT value returned towards baseline levels upon discontinuation of study treatment. The maximum increase ranged from 4.0 to 5.5 x the Upper Limit of Normal (ULN). There were no reported significant changes in bilirubin or alkaline phosphatase. Elevation of ALT requiring withdrawal was also seen among two additional subjects in this study (one in bedaquiline alone group and one in bedaquiline + pyrazinamide group) (13). Data thus far suggests that Pretomanid is not associated with significant hepatic toxicity when given as a single agent for up to 14 days. However, when administered within a regimen with other drugs (for example MOX and PZA) known to be associated with hepatic toxicity, increases in aminotransferase levels have been observed in a few subjects requiring withdrawal from clinical trials.

There were three deaths within an ongoing Phase 3 study evaluating the safety and efficacy of bedaquiline plus linezolid plus Pretomanid in subjects with pulmonary infection of either XDR-TB or treatment intolerant/non-responsive MDR-TB (The Nix-TB Study). Approximately half of the subjects were HIV co-infected, and all had documented XDR-TB. The causes of death have varied based on autopsies and clinical data. Two deaths were related to severe pulmonary tuberculosis, disseminated tuberculosis, acute severe worsening of pulmonary tuberculosis and multi-organ TB. These deaths were both considered by the investigator and sponsor as not related to the study drug regimen. A third death occurred as a result of gastrointestinal bleeding. This was reported by the investigator as possibly related to the investigational drug regimen, although the sponsor considered the event unlikely to be related to the study drug regimen.

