3.3.2 Secondary

- The secondary outcome measures will be:
 - Incidence and severity of serious adverse events reported at any time from the time of study treatment through the end of the study.
 - Incidence and severity of related adverse events at any time from the time of study treatment through Day 12.
 - Summary of physical examination findings (height at baseline, and weight at serial time points from Day of Admission until Day 12), vital signs (serial time points from Day of Admission until Day 12), safety laboratory parameters (Day of Admission, as well as Days 2, 5, and 12), and ECG data (Day of Admission and Day 12).

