4.7 Assessment of Subject Compliance with Study Intervention/Investigational Product

Subject compliance is not anticipated to be an issue. Direct observation of study drug administration will be performed by confinement/hospital unit personnel per their standard procedures. If a subject vomits within two hours of dosing, they will not be redosed, they will not have further study samples taken for PK analysis, and they will be discontinued from the study. This subject could either be replaced or be reconsidered for the study after two weeks following completion of re-screening activities specified in the protocol. If a subject vomits >2 hours of dosing, they will not be redosed, but will continue with study assessments including collection of PK samples.

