5.2.2 Handling of Withdrawals

The primary reason for withdrawal from the study will be recorded on the Study Status data collection form. Subjects will be encouraged to complete the Early Termination Visit. The Early Termination Visit procedures are listed in [Section 6.3.4](#).

Although subjects are free to withdraw at any time or may be withdrawn by the site principal investigator or appropriate sub-investigator at any time, subjects who only receive Pretomanid will be encouraged to remain in this study for safety follow-up assessments.

Every attempt will be made to follow all adverse events, including unsolicited non-serious adverse events, serious adverse events, and new onset chronic medical conditions, ongoing at the time of early withdrawal through resolution as per applicable collection times defined for the specific type of adverse event.

In the case of subjects who fail to appear for a safety follow-up assessment, extensive effort (i.e., three documented contact attempts via phone calls, e-mails, etc., made on separate occasions and followed by a certified letter if possible) will be made to locate or recall them, or at least to determine their health status. These efforts will be documented in the subject's records.

Subjects may be replaced if they vomit study drug within two hours of dosing, if they withdraw, are withdrawn or terminated from this study or are lost to follow-up prior to completion of Day 5 (Visit 04) when the last PK samples are obtained.

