6.4 Unscheduled Study Visits

Unscheduled visits are allowed for the following reasons:

- Management of an AE or SAE.
- Performance of additional laboratory tests for clinically abnormal test values (e.g., confirming elevated levels of liver enzymes).

- Any time the investigator feels that it is clinically appropriate for subject safety.
- Urine or serum pregnancy test.
- PK sampling.

Unscheduled visits will be labeled and documented by the number of the visit the subject just completed, followed by the letter “S” to denote the first unscheduled visit (e.g., 01AS, 02S), the letter “T” to denote second unscheduled visit, etc.

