8.6 Halting Rules

The study will be immediately suspended, and no additional doses administered if any of the following occurs:

1. *Any death occurring during the study that was not the result of trauma or accident.*
2. *2 or more hepatically impaired subjects experience a serious adverse event (other than death), related to study product.*
3. *2 or more non-hepatically impaired subjects experience a serious adverse event (other than death), related to study product.*
4. *3 or more subjects develop a severe (Grade 3) abnormality in the same laboratory parameter, regardless of relatedness to study product. Exception to this would be:*
 - a. *Grade 3 CK elevation without systemic complaints*
 - b. *If there are obvious and acceptable physiological explanations for a Grade 3 abnormality (e.g., Grade 3 hematuria in a menstruating female).*

In this case, the study will be suspended pending review and discussion of all appropriate study data by the Investigator, Sponsor or DMID Medical Monitor, the Independent Safety Monitor, and the Safety Monitoring Committee. The study will not be re-started until all parties have agreed to the course of action to be taken, the IRB and Food and Drug Administration (FDA) have been notified, and IRB approval is obtained.

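### The Early Termination visit has no safety laboratory tests or vital signs, so a dosed subject who leaves before 36 h, including one taken off study for vomiting within 2 h, has no required post-dose liver test

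*Protocol*

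**What the plan says.** Section 6.3.4 of the protocol introduces the visit with "The following assessments will be performed at the early termination visit for subjects who withdraw, or are withdrawn or terminated from this study". Six items follow: interim history, complete physical examination, a symptom review directed at liver disease, concomitant medications, AE/SAE assessment and a pregnancy test. The schedules (protocol Appendix A, SAP Table 3) give 0 mL of blood for Early Termination. In SAP Table 3 the safety laboratory, coagulation and vital-sign rows stop at Visit 05.

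Post-dose chemistry, haematology, INR and urinalysis are scheduled at 36 h (Section 6.3.1), Day 5 (6.3.2) and Day 12 (6.3.3). Nothing of the kind is scheduled between dosing and 36 h.

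For a subject who vomits within two hours of dosing, Section 4.7 (repeated in 7.1.1) states that "they will not have further study samples taken for PK analysis, and they will be discontinued from the study". Section 5.2.2 says that "subjects who only receive Pretomanid will be encouraged to remain in this study for safety follow-up assessments". Section 6.4 permits unscheduled visits, one ground being "Any time the investigator feels that it is clinically appropriate for subject safety".

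**The concern.** Sections 4.7 and 7.1.1 direct a dosed subject out of the study before any post-dose liver test has been drawn, and the exit visit does not draw one. The subject may have cirrhosis, and stays in the safety analysis set because that set contains everyone dosed (Section 10.6.2).

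Two parts of the plan depend on those tests. The secondary outcomes in Section 3.3.2 include "safety laboratory parameters (Day of Admission, as well as Days 2, 5, and 12"), and Section 10.6.5.2 drops subjects with missing values from the change-from-admission summaries. Halting rule 4 in Section 8.6 is triggered when "3 or more subjects develop a severe (Grade 3) abnormality in the same laboratory parameter, regardless of relatedness to study product". A subject with no post-dose sample can appear in neither.

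Symptom review is a weak stand-in. Of the three earlier subjects whose ALT rise led to withdrawal, the protocol's risk section (2.3.1) says: "The elevated transaminases were detected at a scheduled laboratory evaluation and in all three subjects the increased ALT was asymptomatic". The same section lists close liver-enzyme monitoring among the FDA's recommendations and states that this design meets them.

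**Working it through.** **1. Is blood really not planned at Early Termination?** Sum the volumes itemised in Section 7.2.1: 27.5 (screening) + 11.5 (admission) + 10 × 6 (Day 1 PK) + 17.5 (36 h) + 2 × 6 (Days 3 and 4) + 17.5 (Day 5) + 14.5 (Day 12) = 160.5 mL. This reproduces the protocol's stated total with nothing drawn at Early Termination, so the 0 mL entry is consistent across the plan and is not a table error.

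**2. Required post-dose laboratory sets by time of exit** (full schedule: 36 h, Day 5, Day 12):

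| Time of exit | Sets done | Set at exit |
|---|---|---|
| Before 36 h | 0 of 3 | none |
| 36 h to before Day 5 | 1 of 3 | none |
| Day 5 to before Day 12 | 2 of 3 | none |

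**3. Does any other provision require a test?**
- Section 5.2.2 encourages the exit visit and continued safety follow-up; it requires neither.
- Section 6.4 leaves unscheduled visits to the investigator.
- Schedule footnote 10 asks for laboratory tests before discharge, but it is attached to the 36 h cell. The 0 mL entry argues against extending it to early leavers.
- Section 9.6 continues safety follow-up only if the whole study is stopped.

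None makes a post-dose liver test mandatory.

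**4. Weight of one subject.** With 6 planned per impairment group, one untested vomiter is 1/6 = 17% of those dosed. If replaced, as Sections 4.7 and 5.2.2 allow, the share is 1/7 = 14%.

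**5. Could a subject who vomits have meaningful exposure?** Assume a one-compartment model with first-order absorption, using Tmax 4–5 h and half-life 14–20 h from the healthy-volunteer studies in Section 2.1.1.4.2. Solve Tmax = ln(ka/ke)/(ka − ke) for ka, with ke = ln 2/half-life. This gives ka = 0.520–0.828 per hour. The fraction of the eventually absorbed dose already absorbed at time t is 1 − exp(−ka·t):

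| Time of vomiting | No lag | 1 h lag, same Tmax (ka 0.718–1.222/h) |
|---|---|---|
| 30 min | 23–34% | 0 |
| 1 h | 41–56% | 0 |
| 90 min | 54–71% | 30–46% |
| 2 h | 65–81% | 51–71% |

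The 2 h row is the upper end. Exposure after vomiting is reduced, but it cannot be assumed to be nil.

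**6. Blood cost of keeping a vomiter for safety visits.** Safety-only volumes are 17.5 − 6 = 11.5 mL at 36 h, 17.5 − 6 = 11.5 mL on Day 5 and 14.5 mL on Day 12 (including serum pregnancy test), at most 37.5 mL in all. The 11 PK samples from 4 h to 96 h that are no longer drawn save at least 11 × 6 = 66 mL.

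**The case against.** The strongest counter-argument is that the clinical risk is small. The earlier ALT rises arose on repeated dosing, mostly in combination regimens. Section 2.3.1 says pretomanid alone for up to 14 days has not shown significant hepatic toxicity, puts onset in the fatal liver-injury cases at 21 to 24 days of combination treatment, and expects a single dose to lower the risk substantially. No vomiting or dropout rate is given, so the 14–17% is conditional on the event. The absorption model shows possible exposure, not the chance of a missed liver event. All of this stands, and it limits the weight of the point.

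A second objection is that two matters are joined: a panel at a Day 1 exit would be too early to help the vomiter, whose problem comes from Sections 4.7 and 7.1.1 and not from 6.3.4. It would not fill the Day 2, 5 and 12 summaries either. This is also right, and it is why the remedy has two parts with the vomiting rule first.

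Third, existing safeguards count for something. The exit visit has a full examination and a liver symptom review, AEs are followed to resolution, and vital signs are taken at every time point until the subject leaves, so their absence matters little for a Day 1 exit. A subject tested at the investigator's discretion would contribute to the outcome and the halting rule, and that rule needs three subjects. But none of these requires a liver test.

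Finally, keeping a vomiter to 36 h costs an overnight stay or a return visit. That stay and the later visits were already planned for the subject, so the burden is not new.

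**Conclusion.** The concern holds. A dosed subject who leaves before 36 h has no required post-dose AST, ALT, bilirubin or INR, and no early leaver has a laboratory set required at exit. The vomiting rule makes this a foreseeable path. The conclusion on required tests comes directly from the text and schedules. Only the exposure range depends on a model and on healthy-volunteer values, which may not apply in cirrhosis.

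Expected numbers are small and cannot be estimated from the documents. The point concerns safety monitoring and completeness of a secondary outcome; the primary PK comparison is untouched. The change is worth making because it is inexpensive.

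**What to change.** 1. **Sections 4.7 and 7.1.1.** For vomiting within 2 h, stop PK sampling only, and keep the subject in the study for the 36 h (Day 2), Day 5 and Day 12 safety assessments. Replacement stays allowed. The timing fits the option to reconsider such a subject after two weeks: "The final study visit will occur 11 days after Pretomanid administration", three days before that point.

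2. **Section 6.3.4, Appendix A and SAP Table 3.** At Early Termination, add chemistry, haematology, INR, urinalysis and vital signs for dosed subjects who attend and agree. Replace the 0 mL entry with about 11.5 mL (14.5 mL if the pregnancy test is done on serum).

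No new table is needed. Results go into SAP Listings 8–11, and the maximum post-baseline severity rows (for example in SAP Table 26) already accept unscheduled assessments.

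The cost is a short amendment, routine tests and about 11.5 mL per exit set. A vomiter kept for all three safety visits gives at most 37.5 mL, against at least 66 mL of PK draws dropped, and completes the planned stay and visits without contributing PK data. The change does not reach subjects lost to follow-up or those who refuse further tests.
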